#### **11.0 COMPLIANCE**

Whilst patients are in a hospital setting responsibility for compliance will rest with the medical, pharmacy, pharmaceutical science and nursing/technical staff who will be responsible for administering the trial medication. When patients return home, for the first month compliance will be assured by retrieval and counting of all used vials and syringes and completion of a diary to record the time and date of each dose. All empty and unused Coversin vials will be returned to the Sponsor as an additional compliance check.

#### 11.1 Assessment of pharmacokinetics and complement activity

Blood (5ml) samples for CH50 assays and Coversin levels will be collected according to the time schedule presented in Appendix 1. These blood samples will take precedence over all other procedures. Samples will be processed in accordance with Paragraph 20.2.

#### **12.0 ADVERSE EVENTS**

#### 12.1 Adverse Events

All adverse events, whether or not considered to be related to the study drug, will be monitored and reported on at all stages of the study. Adverse events occurring between discharge from hospital and the 1 week follow up visit will be reported at that visit and entered on the adverse event form of the case report forms.

#### 12.2 Definition

An adverse event is any untoward medical occurrence in a patient or clinical investigation subject administered a pharmaceutical product whether or not it is caused by this treatment. An adverse event can therefore be any unfavourable and unintended sign (including an abnormal laboratory finding), symptom, or disease temporally associated with the use of a medicinal product, whether or not considered related to the medicinal product.

Worsening of a medical condition that was present prior to the administration of the study medication will also be considered a new adverse event and reported. Any medical condition present prior to the administration of the study medication which remains unchanged or improved will not be recorded as an adverse event at subsequent visits.

Documentation regarding the adverse event will include the nature, time and date of onset, time and date of resolution, severity, presumed relationship to study medication, action(s) taken, and outcome of any sign or symptom observed by the physician or reported by the subject upon indirect questioning.

## 12.3 Relationship to study medication

The relationship between the AE and the investigational product will be determined by the PI or Sub-PI on the basis of his/her clinical judgement and the following definitions:

- Unrelated: Clinical event with an incompatible time relationship to IMP administration, and that could be explained by underlying disease or other drugs or chemicals or is incontrovertibly not related to the IMP
- **Possibly related**: Clinical event with a reasonable time relationship to IMP administration, and that is unlikely to be attributed to concurrent disease or other drugs or chemicals

Related: Clinical event with plausible time relationship to IMP administration and that cannot be explained by concurrent disease or other drugs or chemicals

The degree of certainty with which an AE is attributed to IMP administration (or alternative causes, e.g. natural history of the underlying disease, concomitant therapy, etc) will be determined by how well the experience can be understood in terms of one or more of the following:

- known pharmacology of the IMP
- reactions of a similar nature have been previously observed with the IMP or this class of drug
- the experience being related by time to IMP administration, terminating with IMP withdrawal or recurring on re challenge
- alternative cause

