#### 3.1 Endpoints

Safety:

- Frequency, type and relationship to treatment of AEs and SAEs
- Out of range laboratory parameters (haematology and chemistry)
- Vital signs
- ECG abnormalities Day 0 Day 90

Primary efficacy endpoint:

• Serum lactic dehydrogenase (LDH) AUC from Day 0 to Day 28 compared with 28 days pre-treatment

Secondary efficacy endpoints:

- Haemoglobin at Day 28 and day 90 and Day 180, absolute and change from baseline
- LDH at days 90 and 180
- Haptoglobin at day 28, day 90 and day 180, absolute and change from baseline
- Dependency on blood transfusion
- Quality of Life at days assessed by the FACIT and EORTC QL-C30 instruments compared to Day 0, day 28, 90 and 180

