## 7.2 Toxicity occurring in two or more patients

In the event of the same or a similar severe adverse event occurring in two or more patients in the trial and which, in the opinion of the PI, is possibly, probably or definitely related to administration of Coversin consideration will be given to halting the trial. A serious adverse event (SAE) occurring in two or more patients which is probably or definitely drug related is

an absolute indication to terminate the trial. Adverse events which are not SAEs but which appear to affect more than one patient will be assessed for their severity, threat to the patients' health and drug relationship and a decision on whether to halt the trial or allow it to continue while keeping the situation under review will be made by the PI and the Sponsor Medical Director.

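### The three causality definitions in Section 12.3 are not exhaustive: a time-compatible event that PNH or another drug could realistically explain fits none of them

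*Combined protocol and SAP*

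**What the plan says.** Section 12.3 asks the PI or Sub-PI to assign relationship using clinical judgement together with three definitions:

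- *Unrelated*: "Unrelated: Clinical event with an incompatible time relationship to IMP administration, and that could be explained by underlying disease or other drugs or chemicals". A second route to this category is an event that "or is incontrovertibly not related to the IMP", with no further condition attached.
- *Possibly related* needs reasonable timing and an event "and that is unlikely to be attributed to concurrent disease or other drugs or chemicals".
- The strongest level is worded as "Related: Clinical event with plausible time relationship to IMP administration and that cannot be explained by concurrent disease or other drugs or chemicals".

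Four factors to weigh follow: pharmacology, earlier reactions with the drug or its class, timing (including withdrawal and rechallenge), and alternative cause. They add no category.

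The result feeds a listed safety endpoint, given in 3.1 and repeated in 6.1: "Frequency, type and relationship to treatment of AEs and SAEs". The synopsis names safety as the primary objective. Causality also appears in the withdrawal and stopping text. For a similar severe event in two or more patients, 7.2 says that if the event, in the PI's opinion, "is possibly, probably or definitely related to administration of Coversin consideration will be given to halting the trial". Sections 5.0 and 7.1 also grade relationship as probable or definite, terms that 12.3 does not define.

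**The concern.** A causality scale should give every event exactly one place. Here *Unrelated* is closed to nearly all time-compatible events, and both other categories are closed to events with a realistic competing cause. The common middle case, where timing fits but something else might equally be responsible, has no home. *Possibly related* is defined by other causes being unlikely, which is a higher bar than its name suggests.

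The trial makes that middle case likely:

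- Coversin is given daily for 6 months (synopsis; 3.0), so most on-treatment events will be time-compatible.
- Patients enter with LDH at least 1.5 times ULN (synopsis), and 12.2 counts worsening of an existing condition as a new adverse event.
- Sections 3.0 and 10.0 add ciprofloxacin, possibly penicillin, and meningococcal vaccines.
- The commonest events that 1.3 reports for eculizumab include headache, nausea and fatigue, which are non-specific.

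The study is open label and non-comparative with 1 to 6 patients. There is no control arm against which to compare incidence, so attribution rests on this classification.

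**Working it through.** There is no figure to reproduce. The check sets the definitions against every combination of three facts:

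- A: timing is incompatible (yes or no).
- Alternative cause: cannot explain the event; could but is unlikely to; could and realistically does. B is true in the last two.
- C: the event is incontrovertibly not related (yes or no).

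That gives 2 × 3 × 2 = 12 combinations. The *Unrelated* sentence can be parsed in two ways: reading 1, (A and B) or C; reading 2, A and (B or C). *Possibly related* is taken as not A with an alternative that could explain the event but is unlikely to. *Related* is taken as not A with no alternative explanation.

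| Timing | Alternative cause | C false (both readings) | C true, reading 1 | C true, reading 2 |
|---|---|---|---|---|
| Compatible | Cannot explain | Related | Unrelated and Related | Related |
| Compatible | Could, unlikely | Possibly | Unrelated and Possibly | Possibly |
| Compatible | Could, realistic | **none** | Unrelated | **none** |
| Incompatible | Cannot explain | **none** | Unrelated | Unrelated |
| Incompatible | Could, unlikely | Unrelated | Unrelated | Unrelated |
| Incompatible | Could, realistic | Unrelated | Unrelated | Unrelated |

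Results:

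1. With C false, 2 of 6 combinations have no category under either reading.
2. Over all 12, reading 1 leaves 2 uncovered and reading 2 leaves 3. Under reading 2, even an incontrovertibly unrelated event with compatible timing and a realistic alternative has no place.
3. Reading 1 also puts two combinations in two categories at once. Both pair C with an alternative cause that is unlikely or impossible, so they will seldom arise.
4. A time-compatible event whose alternative cause is merely conceivable, but unlikely, does fit *Possibly related*. The main gap is confined to realistic alternatives.

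The check treats reasonable, plausible and not incompatible timing as the same thing. Distinguishing them could only open further gaps. If an unlikely alternative is taken to include an impossible one, *Possibly related* and *Related* overlap, but the gaps remain.

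These are counts of logical combinations, not shares of events. The second gap (incompatible timing, no other explanation) should matter less during daily dosing, when few events will have incompatible timing.

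**The case against.** The strongest reply is that the scale is never applied mechanically. The PI or Sub-PI uses clinical judgement and weighs alternative cause, so every event will be coded somehow. The synopsis names one centre and at most 6 patients, so every event can be read individually, and Section 13 plans no test on counts of related events. Section 12.1 has all adverse events reported whatever their cause, and 12.6 sends serious or severe ones to the PI and sponsor at once on the same basis.

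Much of this stands, and it limits the consequences. It does not close the gap: judgement is to be used with the definitions, and they do not say where these events go. Two assessors could code the same event differently, and one assessor could do so on different days.

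A reader might infer more than the documents support:

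- *That related events would be under-counted.* Not shown. The high bar for *Unrelated* could equally push events into *Possibly related*. For infection, the pharmacology and class factors point towards the drug (1.3, 10.0).
- *That the early trigger in 7.2 would miss events.* Not shown. It rests on the PI's opinion without citing 12.3, and 7.2 separately provides for review of non-serious events affecting more than one patient.
- *That a primary safety endpoint fails.* No endpoint has that label. Safety is the primary objective, and the only endpoint called primary is LDH.
- *That a stated share of events is affected.* No figure can be derived. Section 12.2 also keeps unchanged or improved pre-existing conditions out of later adverse event records.

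**Conclusion.** The concern holds in this form: the definitions in 12.3 are wrong as written, not merely short of detail, because two kinds of event meet none of them and nothing elsewhere in the document supplies a rule. The size is 2 of 6 combinations of timing and alternative cause when the event is not incontrovertibly unrelated. The number of patient events affected is unknown. That such events will occur is an inference from daily dosing, active disease and co-medication.

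The consequence is inconsistent coding of relationship to treatment, a listed safety endpoint under the primary objective, with no predictable direction. Collection and prompt reporting of serious or severe events are not affected.

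**What to change.** Reword 12.3 so that each event falls in exactly one category. One version:

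- *Unrelated*: no reasonable time relationship, or clearly explained by another cause.
- *Possibly related*: reasonable time relationship, but concurrent disease or another drug is also a realistic, though not clear, explanation.
- Higher category: reasonable time relationship and other causes unlikely (the wording now under *Possibly related*). This can be a separate level or be merged into *Related*.
- *Related*: as now.

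This covers all six rows of the table. Stating that the alternative is realistic but not clear keeps *Possibly related* separate from its neighbours. A three-level scale would serve equally well if its definitions are complete.

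Then reconcile the causality terms in 5.0, 7.1 and 7.2 with the revised scale, so that every term used there is defined. This is a matter of vocabulary and leaves the stopping rules themselves unchanged. The sponsor and PI should state how each existing term maps to the new levels.

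The cost is protocol wording and one CRF code list. The downside is that more events will probably be coded possibly related. The change is best made before coding starts, since recoding in an open-label trial with outcomes known would be less credible.

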#### 12.4 Serious Adverse Events

A serious adverse event (SAE) is defined as any untoward medical occurrence at any dose that:

- Results in death
- Is life threatening (Note: The term "life threatening" refers to an event in which the subject was actually at risk of death at the time of the event; it does not refer to an event which hypothetically might have caused death if it was more severe).
- Requires in-patient hospitalisation or prolongation of existing hospitalisation. (Note: Complications that occur during hospitalization are AEs. If a complication prolongs hospitalization or fulfils any other serious criteria, the event is serious. Hospitalization for elective treatment of a pre-existing condition that did not worsen from Baseline is not considered to be an AE.)
- Results in persistent or significant disability/incapacity. (Note: The term disability means a substantial disruption of a person's ability to conduct normal life functions. This definition is not intended to include experiences of relatively minor medical significance such as uncomplicated headache, nausea, vomiting, diarrhoea, influenza, or accidental trauma (e.g. sprained ankle) that may interfere or prevent everyday life functions but do not constitute a substantial disruption.)
- Is a congenital abnormality.

Important medical events that may not be immediately life-threatening or result in death or hospitalization but may jeopardize the patient or may require intervention to prevent one of the outcomes listed in the definition above should also usually be considered serious. Examples of such events are intensive treatment in an emergency room or at home for allergic bronchospasm, blood dyscrasias, or convulsions that do not result in hospitalization; or development of drug dependency or drug abuse.

All serious adverse events will be reported to the PI, and the Sponsor within 24 hours of learning of its occurrence. The Sponsor will be responsible for reporting the adverse event to the appropriate regulatory authority and the IRB within the legally specified period. It is important to distinguish between SAEs and severe AEs. Severity is a measure of intensity whereas seriousness is defined by the criteria above. An AE of severe intensity need not necessarily be considered serious. For example, a migraine headache that incapacitates a patient for many hours may be considered a severe AE, whereas a stroke that results in a limited degree of disability may be considered mild, but should be reported as an SAE).

#### 12.5 Severity

The following definitions will apply:

- Mild: Event is noticeable to the patient, but is easily tolerated, requires no additional therapy and does not interfere with the subject's daily activities.
- Moderate:Event causes discomfort or inconvenience, possibly requiring additional therapy, and may interfere with the subject's daily activities.
- Severe: Event is intolerable, necessitates additional therapy or alteration of therapy and interferes with the subject's daily activities.

#### 12.6 Adverse event reporting

All Serious or Severe adverse events, whether or not considered to be drug related, will be reported immediately to the PI and the Sponsor who will be responsible for reporting it/them to the regulatory authority (MHRA) and the Ethics Committee within 24 hours of learning of its occurrence.. They will be recorded on the appropriate CRF with a description of the outcome. Non-serious moderate or mild adverse events will be recorded in the CRFs but need not be reported to the Sponsor at the time unless there are unusual circumstances (e.g. the adverse event was of a completely unexpected nature); they should be reported to the Safety Monitoring Committee within sufficient time for decisions regarding dose escalation to be made.

#### Procedures for reporting a serious adverse event:

Any serious adverse event occurring during the study period should be reported < 24 hours of learning of its occurrence to the Sponsor or its representative listed on the personnel page

and recorded on the appropriate case report forms. All patients experiencing a serious adverse event must be followed up and the outcome reported.

#### Procedures for reporting a suspected unexpected serious adverse reaction (SUSAR)

It is the responsibility of the Sponsor to determine whether a reported SAE fits the classification of a SUSAR and to notify the PI of their decision as soon as possible.

#### Expedited Reporting of Events

It is the responsibility of the Sponsor to determine whether an event requires expedited reporting and to notify the PI of their decision as soon as possible. Where expedited reporting is required, the following procedures should be followed.

#### Fatal or life-threatening SUSARs

It is the responsibility of the Sponsor to report fatal or life-threatening SUSARs to the MHRA and EMA as soon as possible, but no later than 7 calendar days after they first became aware of the reaction.in accordance with Directive.. or per national reg requeirements in particular countries.

The PI is required to notify the EC of any SUSAR as soon as possible, but no later than 7 calendar days after they first became aware of the reaction. Any additional relevant information should be sent within 8 days of the report.

#### Other SUSARs

It is the responsibility of the Sponsor to report other SUSARs to the MHRA and EMA as soon as possible, but no later than 15 calendar days after they first became aware of the reaction.

The PI is required to notify the EC of any other SUSAR as soon as possible, but no later than 15 calendar days after they first became aware of the reaction.

#### 12.7 Follow-up after Adverse Events

Adverse events which have not resolved by the time of anticipated discharge from the clinical unit will be followed up until resolution. If, in the opinion of the PI, they are sufficiently clinically important to necessitate continued observation in a hospital or clinic setting the Sponsor will be informed and arrangements made for continued in-patient care in a suitable facility or referred to their GP. If the subject is able to be discharged they will be followed up in the same way as other subjects in the study or more frequently at the discretion of the PI. All AEs will be recorded in the appropriate pages of the CRFs until there has been full resolution. Any medications (e.g. analgesics) that may be required at the time of discharge will be supplied. Subjects who are discharged from the clinical unit but who have not had full

resolution of the AE (e.g. a skin rash) will continue their own observations at home and make daily records in the diary card, including any worsening or resolution of the AE. Diary cards on which AEs are recorded will be signed by the subject and the PI and will subsequently become part of the CRF record.

#### **13 STATISTICS**

#### **13.1** Statistical Methods

The statistical approach taken will depend on the number of patients recruited.

If less than 4 patients are recruited, each patient will be analysed separately. Changes in the primary efficacy outcome during the period Day 0 to Day 28 will be analysed using linear regression using all measurements in the analysis. Secondary efficacy outcomes measured multiple times will be analysed in an equivalent manner.

If 4 or more patients are recruited, the patients will be analysed as a single group. Differences between specific timepoints (e.g. Day 0 and Day 28) for the primary and secondary efficacy endpoints will be performed using the paired t-test.

Additionally the change in the primary efficacy outcome over time will also be examined using all measurements. Mixed model will be used to allow for repeat measurements from the same patients, with the patient considered as a random effect.

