**Principal PIs Signatures:** 

By my signature, I confirm that my staff and I have carefully read and understand this protocol and agree to comply with the conduct and terms of the study specified herein.

Signature:

[name] Radboud University Medical Centre Nijmegen Netherlands

Signature:

Mu

Date: 11 November 2015.

[name] Radboud University Medical Centre Nijmegen Netherlands

Protocol AK-Study-578 - version 2.0 11 november 2015

CONFIDENTIAL

© Akari Therapeutics Plc

Protocol synopsis				
Protocol Title:	Coversin in paroxysmal nocturnal haemoglobinuria (PNH) in patients with resistance to eculizumab due to complement C5 polymorphisms.			
Protocol Number:	AK Study 578			
Sponsor:	Akari Therapeutics Plc			
	[name]			
	[name]			
	UK			
Investigational Product(s):	Coversin (rVA576) sterile solution for subcutaneous injection 7.2 mg/mL			
Phase of Development:	П			
Indication:	Paroxysmal nocturnal haemoglobinuria			
PI(s):	[name]			
	[name]			
	Department of Haematology			
	Radboud University Medical Centre			
	Nijmegen			
	Netherlands			
Study Center(s):	Radboud University Medical Centre			
	Nijmegen			
	Netherlands			
Objectives:	Primary Objective: Safety of Coversin (rVA576).			
	Secondary Objectives: Efficacy of Coversin in the treatment of patients with PNH resistant to eculizumab.			
Study Design:	Open label, non-comparative			
Planned Number of Subjects:	Minimally 1 and maximally 6			
	Patients with PNH, male or female, 18 years or older with proven resistance to eculizumab due to complement C5 polymorphisms			
Subject Population:				
Subject Population: Diagnosis and Main				
Diagnosis and Main Criteria for Inclusion and	resistance to eculizumab due to complement C5 polymorphisms			
Diagnosis and Main	resistance to eculizumab due to complement C5 polymorphisms Inclusion Criteria:			
Diagnosis and Main Criteria for Inclusion and	
 
resistance to eculizumab due to complement C5 polymorphisms
 
Inclusion Criteria:
 
Patients with known paroxysmal nocturnal haemoglobinuria (PNH)
 
			

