## **Protocol synopsis**

	Exclusion Criteria:		
	• Pregnancy (females)		
	• Known allergy to ticks or severe reaction to arthropod venom (e.g. bee or wasp venom)		
	• Failure to satisfy the PI of fitness to participate for any other reason		
Treatment Regimen:	Single ablating dose of 0.57mg/kg per subject followed by daily maintenance doses. The initial maintenance dose will be 25% of the ablating dose. If this is insufficient to maintain complement activity at $\leq 10\%$ of baseline (pre-treatment) level after 5 days of treatment the daily maintenance dose will be increased by doubling until that level of inhibition is achieved. In the event of 100% inhibition being achieved the dose may be titrated downwards at the PI's discretion until a satisfactory clinical result is obtained. If at any point in treatment complement activity (CH50) is 50% of baseline or more a further ablating dose of 0.57mg/kg should be given. An increased daily maintenance dose may be required in the event of intercurrent infection or illness. CH50 level should be checked in the event of deteriorating clinical response manifested by rising serum LDH.		
Duration of Treatment:	Patients will undergo an initial period of 6 months treatment according to this protocol. At the expiry of this period, and on the recommendation of the PI, patients will have the option of remaining on long-term Coversin therapy and will enter the long term follow-up study.		
Endpoints:	Efficacy Endpoints:		
	Primary: Reduction in serum LDH from day 0 – Day 28		
	Secondary: Hb, haptoglobin, Fatigue (FACIT), Quality of Life (EORTC QL-C30), PNH RBC clone size, Transfusion requirement		
	Safety Endpoints:		
	Adverse events, ECG, Laboratory results, Vital signs.		
Statistical Methods:	Descriptive statistics		

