#### 6.1 Endpoints

Primary Efficacy Endpoint:

• Significant reduction in mean serum LDH from Day 0 (pre-dose) to Day 28 (AUC)

Secondary Efficacy Endpoints:

- Change in LDH from Day 0 (pre-dose) at monthly intervals after Day 28
- Change in proportion of PNH clone Day 0 Day 90
- Change in mean Hb Day 0 Day 90
- Change in mean Hp Day 0 Day 90
- Change in FACIT score Day 0 day 28- Day 90 Day 180
- Change in EORTC QLQ C30 score Day 0 -Day 28-Day 90 Day 180

Safety Endpoints:

- Frequency, type and relationship to treatment of AEs and SAEs
- Out of range laboratory parameters (haematology and chemistry)
- Vital signs
- ECG abnormalities Day 0 Day 90

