#### **13.3** Significance Level

For all comparisons p < 0.05 will be considered significant.

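### With fewer than 4 patients, the Section 13.1 regression gives an LDH slope, not the AUC comparison with the pre-treatment period that Section 3.1 makes the primary efficacy endpoint

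*Combined protocol and SAP*

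**What the plan says.** Planned enrolment is "Minimally 1 and maximally 6" (synopsis). Section 13.1 splits the analysis by the number recruited. Below 4, each patient is analysed alone: "Changes in the primary efficacy outcome during the period Day 0 to Day 28 will be analysed using linear regression using all measurements". The predictor, the scale of LDH, the parameter tested and the sidedness are not stated. The next sentence extends the method: "Secondary efficacy outcomes measured multiple times will be analysed in an equivalent manner".

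The primary efficacy endpoint is worded in three ways:

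- Synopsis: "Primary: Reduction in serum LDH from day 0" to Day 28, with no AUC and no pre-treatment window.
- Section 3.1: "Serum lactic dehydrogenase (LDH) AUC from Day 0 to Day 28 compared with 28 days pre-treatment".
- Section 6.1: "Significant reduction in mean serum LDH from Day 0 (pre-dose) to Day 28 (AUC"; AUC is named, but no 28-day pre-treatment comparator.

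On inference, Section 13.3 says "For all comparisons p < 0.05 will be considered significant", while the synopsis gives the statistical methods as "Descriptive statistics". Section 13 does not say how an AUC is calculated or set against a pre-treatment period.

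**The concern.** The stated analysis does not estimate the stated endpoint. A Day 0-28 AUC is one number per patient, and Section 3.1 compares it with a second number from before treatment. A regression confined to Day 0-28 has no pre-treatment data, so no choice of predictor recovers that comparison. Taken as LDH on day, it estimates an average daily change.

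Two further problems follow. Section 6.0 expects control by day 5, meaning an early fall and then a plateau, which a straight line fits poorly. Ordinary regression also treats serial values from one patient as independent, so its p-value is unreliable if they are correlated.

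The branch for fewer than 4 patients is a planned possibility and may carry the whole efficacy result. Section 6.1 asks for a significant reduction and Section 13.3 sets the threshold without exception. On the ordinary reading, the slope's p-value would then decide whether the primary efficacy endpoint was met.

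**Working it through.** The documents give no sample size calculation, power or LDH variability, so there is no figure of theirs to reproduce. The sampling schedule (Appendix 1) is not in the text available. Step 1 needs no schedule. Steps 2 to 4 are illustrations on assumed inputs, not bounds.

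**Step 1. The slope ignores pre-treatment LDH.** Assume LDH falls linearly from 5 to 1.2 xULN by day 5 and then stays flat.

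- AUC = 5 × (5 + 1.2)/2 + 23 × 1.2 = 15.5 + 27.6 = 43.1 xULN-days.
- Time-weighted mean = 43.1/28 = 1.539 xULN.
- Ratio to the pre-treatment mean: 1.539/3 = 0.51; 1.539/5 = 0.31; 1.539/8 = 0.19.

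The Day 0-28 values are the same in all three cases, so the slope and p-value are too.

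**Step 2. Pass or fail depends on visits and scale.** Assumed schedules: 7 visits (days 0, 2, 5, 7, 14, 21, 28); 8 visits (adding day 1); 10 visits (daily to day 5, then 7, 14, 21, 28); and daily. The fits are least squares of LDH on day without noise, with two-sided p shown as raw / log LDH. The pre-treatment mean is taken as 5 xULN.

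| LDH course | 7 visits | 8 visits | 10 visits | Daily | AUC ratio |
|---|---|---|---|---|---|
| Linear 5 to 1.2 by day 5, then flat | 0.118 / 0.110 | 0.055 / 0.051 | 0.036 / 0.023 | 0.0004 / 0.0002 | 0.31 |
| Exponential 5 to 1.2, half-life 1.2 days | 0.143 / 0.092 | 0.075 / 0.042 | 0.073 / 0.030 | 0.0013 / 0.0002 | 0.29 |

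With no noise, these p-values reflect only how badly a line fits a plateau. The AUC ratio barely moves.

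**Step 3. Slope and AUC can disagree.** The pre-treatment AUC is 5 × 28 = 140 xULN-days.

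- *Ranking.* A fall from 5 to 1.5 xULN with a 1-day half-life has AUC 47.0 (47.0/140 − 1 = −66%). A straight-line fall from 5 to 1.5 has AUC 3.25 × 28 = 91.0 (−35%). At 8 visits the slopes are −0.077 and −0.125 xULN/day, so the better AUC has the shallower slope.
- *Relapse.* LDH falls from 5 to 1.5 by day 3, holds to day 14, then returns to 5 by day 28. AUC = 9.75 + 16.5 + 45.5 = 71.75 (−49%). The slope is positive on all four schedules.
- *Rise then fall.* LDH is 5, 5.5, 6, 6.5, 7, 7, 7, 6, 4, 3 xULN at the 10 visits. AUC = 24 + 21 + 45.5 + 35 + 24.5 = 150; mean 150/28 = 5.36, which is 7% above 5. The slope is −0.104 xULN/day with p = 0.018 / 0.009. At 8 visits p = 0.053 / 0.030, and at 7 visits 0.057 / 0.037.

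**Step 4. Serial correlation.** With no drug effect and an assumed day-to-day (AR(1)) correlation of 0.5 to 0.9, the share of runs with p < 0.05 (nominal 5%, 40,000 runs each) was:

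| | 7 visits | 8 visits | 10 visits | Daily |
|---|---|---|---|---|
| Either direction | 7-26% | 9-32% | 11-40% | 25-63% |
| Falling slope only (nominal 2.5%) | 3-13% | 5-16% | 6-20% | 12-32% |

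**The case against.** **Which wording governs.** The regression is close to the synopsis wording, so the mismatch could be blamed on the three unreconciled endpoint texts. That is part of the problem, but it does not rescue the plan: neither AUC version is estimated.

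**The p-value.** No sentence says that a slope is tested, and the synopsis is purely descriptive. Applying p < 0.05 to the slope is therefore a reading. It is the ordinary one, given Sections 6.1 and 13.3.

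**The illustrations.** These points stand. The rise-then-fall curve is contrived: it runs against the expected control by day 5, ends below its start, and misses 0.05 on the raw scale at 7 and 8 visits. The two curves in the Step 2 table are rapid responders, whereas Section 6.0 also foresees slower falls, which a line fits better. Only about half of the two-sided false positives are falling slopes. None of this touches Step 1.

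**Scope.** With 4 or more patients, the paired t-test between timepoints also computes no AUC. That similar gap does not undo the correction here.

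**Importance.** Safety is the primary objective, continuation is a clinical decision, and a large fall would be plain in the raw LDH values. This limits the severity but does not make the stated analysis right.

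**Conclusion.** The concern holds. Followed as written, the branch for fewer than 4 patients cannot produce the Section 3.1 endpoint, because its data window excludes the comparator. This rests on the text alone. Calling the result a slope assumes that day is the predictor, which is the natural reading.

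The schedule-free size is that AUC ratios from 0.19 to 0.51 share one slope and one p-value. The dependence of p on visits and scale, the disagreements between slope and AUC, and the inflated error rates rest on assumed schedules, LDH courses and correlations. They show what can happen, not what will.

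It should be fixed before the LDH data are read. It affects the primary efficacy endpoint, not the primary safety objective.

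**What to change.** In the branch of Section 13.1 for fewer than 4 patients, replace the regression of the primary endpoint with wording such as:

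> For each patient, the time-weighted mean LDH for Day 0-28 (trapezoidal AUC divided by days) will be divided by that for the 28 days pre-treatment and reported descriptively with the individual LDH plot. No p-value will be calculated.

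Also:

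- State which pre-treatment LDH values are used.
- Use one wording of the primary efficacy endpoint in the synopsis, Section 3.1 and Section 6.1, and drop *Significant* from it for this branch.
- Give the secondary outcomes their own sentence, since they are now tied to the regression. The absolute values and changes from baseline already listed in Section 3.1 would serve.

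Omitting the p-value is one reasonable choice, and it agrees with the synopsis. If a test is kept, specify its predictor, scale, sidedness and handling of serial correlation; no performance is claimed for such a test here.

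The cost is a few sentences in four places, with no data beyond the pre-treatment LDH that Section 3.1 already requires. The downsides are that per-patient p-values are lost and that the ratio is only as good as the pre-treatment LDH values available.
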